#### **6.2.4.2. Cisplatin (Total and Free)**

PK parameters for cisplatin (total and free) will be estimated using noncompartmental and/or compartment methods, if needed. Analyses will include  $C_{max}$ , time to  $T_{max}$ ,  $AUC_{inf}$ ,  $t_{1/2}$ ,  $CL$ , and  $V_z$  as data permit. Dose-normalized parameters [eg,  $C_{max}$  (dn),  $AUC_{inf}$  (dn)] will be reported as appropriate. Descriptive statistics for the PK parameters for cisplatin will be provided in tabular form. Cisplatin plasma concentrations will be summarized descriptively (n, mean, SD, CV, median, minimum, maximum, geometric mean, its associated CV, and 95% CI) by nominal time. Individual patient and median profiles will be presented on both linear-linear and log-linear scales.

Additionally, cisplatin PK (total and free) will be evaluated following avelumab or placebo dosing by comparing the overall geometric mean ratios of  $C_{max}$  and  $AUC_{inf}$  on Day 1 of the CRT Phase in Arm A to Day 1 of the CRT Phase in Arm B.

Pharmacokinetic parameters for cisplatin (total and free) will be taken from observed values or derived from plasma concentration-time data as described in Section 3.2.4.

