**Arm A: Avelumab + SOC CRT**  
**Arm B: Placebo + SOC CRT**
- In both treatment arms, study treatment will be initiated with a Lead-in avelumab/placebo Phase followed by a Chemoradiotherapy (CRT) Phase and a Maintenance Phase. In both arms, BSA must be calculated prior to each cisplatin administration and patient must be weighed prior to each avelumab/placebo administration. Specific therapies to be administered include the following:
- Lead-in Phase: avelumab 10 mg/kg (Arm A) or placebo (Arm B) administered on Day 1 (7 days prior to the start of the CRT phase).
  - CRT Phase: avelumab 10 mg/kg (Arm A) or placebo (Arm B) administered on Days 8, 25, and 39 in combination with cisplatin 100 mg/m^2 on Days 1, 22, and 43 plus intensity modulated-radiation therapy (IMRT) 70 Gy/35 fractions/7 weeks; 1 fraction/day, 5 fractions/week. **Cisplatin should be administered on a Monday or Tuesday if feasible to maximize overlap with IMRT.** The Day 43 dose of cisplatin can be given any time up to 5 days after the end of radiation therapy.
  - Maintenance Phase: avelumab 10 mg/kg (Arm A) or placebo (Arm B) administered Q2W for 12 months. The Maintenance Phase starts following completion of CRT Phase (ie, 2 weeks following completion of CRT).
- Patient weight should be verified prior to dose calculation for each of the study treatments.  
See Section 5.5.1.5 and 5.5.2.1 for mandatory premedications to be administered with avelumab/placebo and cisplatin, respectively.
19. **Avelumab Pharmacokinetics:** Blood samples (3.5 mL) for avelumab PK will be collected in all patients: pre-dose (within 2 hours before the start of avelumab/placebo infusion) and at the end of infusion (immediately before until 10 minutes after the end of avelumab/placebo infusion) on Days 1 of the Lead-in Phase and Days 8, and 25 of the CRT Phase.
20. **Cisplatin Pharmacokinetics:** Blood Samples (5 ml) for cisplatin PK (total and free) will be collected in a total of 24 patients (12 patients in Arm A and 12 patients in Arm B) at selected sites at pre-dose, mid-infusion, end of infusion (immediately before the end of cisplatin infusion), and 3, 4, and 24 hours post start of cisplatin infusion on Day 1 of the CRT Phase.

- |     |   |
|-----|---|
| 21. | CCI [REDACTED] CCI [REDACTED]   |

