#### **5.4.2. Cisplatin**

All patients will receive cisplatin (100 mg/m^2) administered IV on Days 1, 22, and 43 of the CRT Phase (note: cisplatin given within 48 hours of the scheduled days is acceptable). The actual dose of cisplatin administered should be based on actual body surface area (BSA).

In case of obesity (body mass index (BMI) >30 kg/m^2), actual BSA will still be used according to the ASCO recommendation published in the Journal of Clinical Oncology, 2012: Appropriate Chemotherapy Dosing for Obese Patients with Cancer ([Appendix 8](#)).

Cisplatin is to be given on a Q3W schedule of 100 mg/m^2 (a weekly dosing schedule is not allowed on protocol) on Day 1, 22 and 43 of the CRT phase. The 100 mg/m^2 dose may be split over 2 to 4 consecutive days (eg, 50 mg/m^2 on 2 consecutive days up to 25 mg/m^2 over 4 consecutive days) if that is the institutional standard way of delivering the Q3W cisplatin dosing. It is recognized that some patients will not be able to receive the 3rd dose of cisplatin and this is not a protocol deviation.

Complete information for cisplatin may be found in the SRSD, which for this study is the cisplatin package insert.

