**Table 3. PK Parameters to be Determined for Avelumab and Cisplatin**

Parameter	Definition	Method of Determination
$AUC_{inf}$	Area under the plasma concentration-time profile from time zero extrapolated to infinite time	$AUC_{last} + (C_{last}/k_{el})$ where $C_{last}$ is the predicted plasma concentration at the last quantifiable time point estimated from the log-linear regression analysis, and $k_{el}$ is the terminal phase rate constant calculated by linear regression of the log-linear concentration-time curve. Only those data points judged to describe the terminal log-linear decline will be used in the regression.
$C_{max}$	Maximum observed plasma concentration	Observed directly from data
$T_{max}$	Time for $C_{max}$	Observed directly from data as time of first occurrence
$t_{1/2}^a$	Terminal half-life	$\text{Log}_e(2)/k_{el}$ , where $k_{el}$ is the terminal phase rate constant calculated by a linear regression of the log-linear concentration-time curve. Only those data points judged to describe the terminal log-linear decline were used in the regression.

$C_{\text{trough}}$	Predose concentration during multiple dosing	Observed directly from data
CL	Clearance	Dose / $AUC_{\text{inf}}$
$V_z^a$	Apparent volume of distribution	Dose / ( $AUC_{\text{inf}} \cdot k_{\text{el}}$ )
$AUC_{\text{inf}}(\text{dn})^a$	Dose normalized $AUC_{\text{inf}}$	$AUC_{\text{inf}} / \text{Dose}$
$C_{\text{max}}(\text{dn})$	Dose normalized $C_{\text{max}}$	$C_{\text{max}} / \text{Dose}$

a If data permit

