#### **6.5.3.2. Exposure to Cisplatin**

Cisplatin is to be administered only in the CRT Phase. Three doses of cisplatin (100 mg/m^2) are planned to be administered on Days 1, 22, and 43 of the CRT Phase.

**Intended duration of cisplatin treatment** in CRT Phase (weeks) = 63/7 = 9 weeks

**Duration of exposure to cisplatin** in the CRT Phase (weeks) =

$$(\text{last dose date of cisplatin} - \text{first dose date of cisplatin} + 21) / 7$$

**Cumulative cisplatin dose** (mg/m^2) is the sum of the actual doses of cisplatin received in the CRT Phase.

**Actual Dose Intensity (DI)** for cisplatin in the CRT Phase =

$$[\text{cumulative dose (mg/m}^2\text{)}] / [\text{intended duration of cisplatin treatment (weeks)} / 9] \text{ (mg/m}^2\text{/9-weeks)}$$

**Relative Dose Intensity (RDI)** for cisplatin in the CRT Phase is calculated as follows:

- Intended DI (mg/m^2/9-weeks) = 300 (mg/m^2/9-weeks)
- RDI (%) = 100 × [actual DI] / [intended DI] = 100 × actual DI / 300.

The summary of treatment exposure and compliance for cisplatin will include the following information:

- Duration of exposure to cisplatin (weeks);

- Total number of doses a received;
- Cumulative dose (mg/m^2);
- Actual DI (mg/m^2/9-weeks);
- RDI (%).

a Per protocol, cisplatin dose can be split over a period of 2 to 4 consecutive days. Therefore, if cisplatin is given consecutively over 2-4 days, this will be viewed as a split dose. Split doses will be summed up and categorized as a single dose.

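### The arm comparison of cisplatin exposure uses Cmax and AUCinf without dose normalization, although permitted split dosing lets the Day 1 dose differ fourfold

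*SAP*

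**What the plan says.** SAP 6.2.4.2 states that "cisplatin PK (total and free) will be evaluated following avelumab or placebo dosing by comparing the overall geometric mean ratios of" two parameters, Cmax and AUCinf, with Arm A set against Arm B on CRT Day 1. Protocol 9.3.2.9.2 says the same. SAP Table 3 has separate entries for Cmax(dn) and AUCinf(dn), each being the parameter divided by Dose. In the SAP's own notation, therefore, the comparison is not normalized. Of the normalized parameters, SAP 6.2.4.2 says only that they "will be reported as appropriate. Descriptive statistics for the PK parameters for cisplatin will be provided in tabular form"; it does not tie them to the arm comparison.

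Protocol 5.4.2 says that the 100 mg/m² "dose may be split over 2 to 4 consecutive days", "if that is the institutional standard way of delivering the Q3W cisplatin dosing". Its examples run from 50 mg/m² on each of two days to 25 mg/m² on each of four.

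Footnote 20 of the protocol's first Schedule of Activities table (Table 2) collects cisplatin samples in 24 patients, 12 per arm, at selected sites. Sampling runs from before the infusion to "24 hours post start of cisplatin infusion on Day 1 of the CRT Phase". Neither document limits this subset to patients given the dose in one infusion.

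Split dosing is addressed in the exposure section, SAP 6.5.3.2: "Split doses will be summed up and categorized as a single dose". That sentence is a footnote to the number of doses received.

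**The concern.** Cisplatin pharmacokinetics is a named secondary objective, and protocol 1.2.3.3.1 notes that the combination of avelumab, radiotherapy and cisplatin was not studied in nonclinical pharmacokinetic work. The ratio in SAP 6.2.4.2 is the only arm contrast of cisplatin exposure that the plan spells out; the comparison in SAP 6.2.4.1 looks at avelumab after cisplatin.

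A patient on a 2-day or 4-day split contributes Cmax and AUCinf from a half or a quarter of the dose. Splitting follows institutional habit, so it clusters by site, and protocol 5.1 stratifies randomization by T stage, nodal stage and HPV status, not by site. Toxicity modifications apply only to Days 22 and 43 (protocol 5.5.2.2), so splitting is the permitted reason for different Day 1 doses per m². With 12 patients per arm, a few split-dose patients more in one arm could look like an interaction or mask one.

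**Working it through.** **Inputs from the documents.** 12 patients per arm; Day 1 dose of 100 mg/m², or a fraction f of it, with f = 0.5 (2-day split) or 0.25 (4-day split). The plan gives no alpha, margin, variability or precision for this comparison, so there is no figure of its own to reproduce.

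**Assumptions.** Exposure proportional to the Day 1 dose; no avelumab effect. The shares, CV and band below are illustrative and are not in the documents.

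**1. Effect of an imbalance.** If Arm A has k more split-dose patients than Arm B, the difference in mean log exposure is (k/12)·ln f, so the geometric mean ratio (GMR, A/B) is f^(k/12).

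| k | f = 0.5 | f = 0.25 |
|---|---|---|
| 1 | 0.94 | 0.89 |
| 2 | 0.89 | 0.79 |
| 3 | 0.84 | 0.71 |
| 4 | 0.79 | 0.63 |

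An excess in Arm B gives the reciprocals, for example 1/0.79 = 1.26.

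**2. How likely an imbalance is.** With independent splitting, k is the difference of two Binomial(12, p) counts.

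| Split share p | P(\|k\| ≥ 2) | P(\|k\| ≥ 4) |
|---|---|---|
| 10% | 29% | 1.8% |
| 20% | 44% | 7.1% |
| 30% | 50% | 11.6% |
| 50% | 54% | 15.2% |

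If whole sites split (assumed: 4 sites of 6 patients, each site splitting with probability 25% to 50%), the two probabilities are 45–58% and 12–16%.

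**3. Added variance.** Var(log GMR) = (2/12)·[s² + p(1−p)(ln f)²]. For an assumed between-patient CV of 30%, s² = ln(1.09) = 0.086.

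- No splitting: √(0.086/6) = 0.12.
- p = 20%, f = 0.5: √((0.086 + 0.16 × 0.480)/6) = 0.16.
- p = 20%, f = 0.25: √((0.086 + 0.16 × 1.922)/6) = 0.26.

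Simulation (20,000 runs per scenario) gave 0.12, 0.17 and 0.26. At this CV, the chance that a null GMR falls outside an assumed 0.80–1.25 band was 6% with no splitting, 18–20% with 20–30% on a 2-day split, and 39–43% with 20–30% on a 4-day split.

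**4. Bias or variance?** In the same simulation, with shares of 0–30% and CVs of 20–40%, a two-sided 5% t-test on log values rejected in 4.8–5.2% of runs. Averaged over randomizations there is no systematic shift.

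**5. What normalization does.** Under proportionality, exposure divided by the Day 1 dose no longer depends on f, so the factor f^(k/12) becomes 1 for every k. Division by the summed course dose of 100 mg/m² leaves f^(k/12) unchanged. The definition of Dose therefore decides whether normalization helps, and Table 3 does not define it for a split course.

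**The case against.** The strongest reply is that this is a descriptive look in 24 patients, with no hypothesis, margin or decision rule, and that dose-corrected results are already planned: the normalized parameters at discretion, and CL, which Table 3 defines as Dose/AUCinf. A reader of the report could notice a dose artefact. That stands, and it limits the importance of the point. It does not change the parameters on which the comparison is specified, and it leaves the choice of scale until results are known.

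It is also fair that the selected sites may all give single-day infusions.

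Four stronger inferences are tempting, and the documents do not support them:

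- *The comparison is biased or its error rate inflated.* Step 4 shows otherwise; the harm is extra variance in the one ratio that is observed.
- *The 24-hour sample is contaminated by the second daily infusion.* Footnote 1 of Table 2 places assessments before dosing unless otherwise indicated, so this sample would precede that infusion.
- *The exclusion rule in SAP 5.3.1.2 cannot reach split-dose patients.* It covers any known biased parameter estimate, and deviation from the assigned dose level is only its example. Whether it would be applied to a permitted split is not stated.
- *CL will be overstated two- to fourfold.* That would follow if the summed dose were divided by a Day 1 AUC. But the summing rule belongs to the exposure count, and SAP 6.2.4.2 refers PK derivations to SAP 3.2.4. The gap is an undefined Dose, not a stated error.

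**Conclusion.** The point holds as a weakness in a secondary, descriptive PK comparison. As specified, the ratio can be moved by imbalance in a permitted dosing practice: to 0.89 or 0.79 for an excess of two split-dose patients in Arm A, and to 0.79 or 0.63 for an excess of four, with reciprocals in the other direction. These sizes rest on dose proportionality and on split-dose patients being in the subset at all; the documents give no frequency, and if there are none the problem does not arise. The primary endpoint is untouched.

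**What to change.** In SAP 6.2.4.2 and protocol 9.3.2.9.2:

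1. Make the Arm A/Arm B comparison on Cmax(dn) and AUCinf(dn), which Table 3 already defines.
2. Define Dose, for these parameters and for CL, as the amount infused on Day 1, not the summed course dose of SAP 6.5.3.2.
3. Keep the raw comparison as supportive.
4. Add a sensitivity analysis limited to patients given the full dose in one infusion, and list the split-dose patients.

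The cost is minor wording in both documents and one extra small analysis. The main comparison loses no patients, because the restriction applies only to the sensitivity analysis. It does rely on dose proportionality, and for Cmax on similar infusion times, which the sensitivity analysis helps to check. No change to dosing is implied.

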#### **6.2.5. Population pharmacokinetic endpoints**

Pharmacokinetic and pharmacodynamic data from this study may be analyzed using modeling approaches and may also be pooled with data from other studies to investigate any association between avelumab exposure and biomarkers or significant safety/efficacy endpoints. The results of these analyses, if performed, may be reported separately.

In addition, the relationship between exposure and efficacy and safety endpoints may be explored, as necessary, based on emerging efficacy and safety data. The analysis details will be provided in the Population Modeling Analysis Plan. The results of these modeling analyses may be reported separately from the clinical study report. The analyses will include patients in both the FAS and the safety analysis set.

#### **6.2.6. Biomarker endpoints**

There are two sets of biomarkers, those collected at screening (pre-treatment tumor sample), and the optional tumor sample after one dose of avelumab. The optional tumor samples will be analyzed separately.

Summary statistics for pre-treatment biomarkers will be presented by treatment arm and overall. Summary statistics for on-treatment biomarkers will additionally include the ratio to baseline for continuous biomarkers, and a contingency table for non-continuous biomarkers, as appropriate.

Continuous biomarkers will be split at the median ( $<$  and  $\geq$  median), and will be included as a covariate in an exploratory Kaplan-Meier analysis for PFS, as described in Section 6.1.1.1; no other covariates will be included. Non-continuous biomarkers will either be split at an appropriate point in their distribution, and classified as above and below the split (0,1), or the actual categories will be included in the survival analysis.

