#### Secondary Objectives

- To compare the overall survival (OS) of avelumab in combination with SOC CRT vs SOC CRT alone;
- To evaluate the anti-tumor activity of avelumab in combination with SOC CRT and SOC CRT alone;
- To evaluate the overall safety and tolerability profile of avelumab in combination with SOC CRT and SOC CRT alone;
- To evaluate the PK of avelumab;

- To evaluate the PK of cisplatin (total and free);
- To assess avelumab ADAs;
- To evaluate the effect of avelumab in combination with SOC CRT and SOC CRT alone on patient-reported outcomes (PROs) of disease-related symptoms and health related quality of life (HRQoL);
- To evaluate candidate immune-related predictive biomarkers of sensitivity or insensitivity to treatment with avelumab in combination with SOC CRT in pretreatment tumor samples (eg, PD-L1 expression);
- To evaluate candidate immune-related predictive biomarkers of sensitivity or insensitivity to treatment with avelumab in combination with SOC CRT in tumor samples (eg, PD-L1 expression) after one dose of avelumab in patients who provide this optional biopsy.

CCI

[figure not shown]

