**Table 4. Biomarker Definition and Determination**

Parameter	Definition	Method of Determination
PD-L1	Protein expression using immunohistochemistry assay	VENTANA PD-L1 (SP263) Assay
Tumor infiltrating CD8+ lymphocytes	The number of CD8+ cells per unit area and the percent of counted cells that are scored as CD8+	Pathologist, assisted by image analysis

CCI [REDACTED]

[REDACTED]

[REDACTED]

[REDACTED]

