### 6.4. Subset Analyses

Subset analyses will be performed for PFS, OS, uOR and DR based on the FAS for the subgroups defined below.

The following subgroups will be defined and used for analyses:

- Randomization stratification factors
  - Tumor (T) stage (<T4 vs T4; T4=Reference);
  - Nodal (N) stage (N0/N1/N2a/N2b vs N2c/N3; N2c/N3=Reference);
  - HPV status (positive vs negative; negative=Reference) as measured by p16 expression by IHC.

- Age
  - Age < 65 years (Reference);
  - Age ≥ 65 years.
- Gender
  - Male (Reference);
  - Female.
- Race
  - White (Reference);
  - Asian;
  - Black or African American;
  - Other.
- Ethnicity
  - Hispanic or Latino;
  - Not Hispanic or Latino (Reference).
- Pooled Geographical Region
  - North America;
  - Western Europe (Reference);
  - Eastern Europe;
  - Asia;
  - Rest of the World (Australasia, Latin America, Africa and/or Middle East will be included as additional subgroups if including > 10% of the overall randomized population).
- ECOG Performance Status at Baseline
  - 0 (Reference);
  - 1.
- Subsite of Primary Diagnosis
  - Oral cavity (Reference);
  - Oropharynx;
  - Larynx;
  - Hypopharynx;
  - Other.

Subset analyses for PFS, OS and DR will use the primary censoring rules described in Sections 6.1.1.1 and 6.2.2.1. All the subgroup analyses are exploratory. Treatment arms will be compared for PFS and OS using a 2-sided unstratified log-rank test for each subgroup

level and the unstratified HR and its corresponding 95% CI will be computed per subgroup level.

All the subgroup analyses will be exploratory; no adjustment for multiplicity will be performed. In the case of a low number of patients within a category (<5% of the randomized population), the categories will be pooled.

To assess the heterogeneity of treatment effects for PFS and OS across the subgroup levels, two Cox regression model will be fitted with PFS or OS, respectively, as the dependent variable and subgroup, treatment, and with and without the treatment-by-subgroup interaction as explanatory variables.

- Model 1: factors + treatment + subgroup
- Model 2: factors + treatment + subgroup + treatment×subgroup-variable

A p-value for the interaction test (Wald's test) will be provided together with the HR and corresponding 95% CI for the interaction model parameter.

The HR for PFS and OS and corresponding 95% CIs for all subgroups will also be presented in a forest plot.

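### SAP 6.2.6 relates continuous tumor biomarkers to PFS only after a median split; adding an exploratory Cox model on the measured scale would keep information that the split discards

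*SAP*

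**What the plan says.** A secondary objective in SAP 2.1 is: "To evaluate candidate immune-related predictive biomarkers of sensitivity or insensitivity to treatment with avelumab" in combination with standard chemoradiotherapy. It covers pre-treatment samples and, separately, the optional biopsy after one dose.

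SAP 3.2.6, Table 4, defines CD8 on a continuous scale: "The number of CD8+ cells per unit area and the percent of counted cells that are scored as CD8" positive. PD-L1 is given only as "Protein expression using immunohistochemistry assay", with no percentage, score or scale.

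SAP 6.2.6 then sets the analysis:
- For continuous markers: "Continuous biomarkers will be split at the median". The resulting variable "will be included as a covariate in an exploratory Kaplan-Meier analysis for PFS, as described in Section 6.1.1.1; no other covariates will be included".
- For other markers: "Non-continuous biomarkers will either be split at an appropriate point in their distribution", or the actual categories are used.
- On the measured scale: descriptive statistics, and "Summary statistics for on-treatment biomarkers will additionally include the ratio to baseline for continuous biomarkers".

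SAP 6.4 plans a heterogeneity analysis for PFS and OS ("A p-value for the interaction test (Wald's test) will be provided"), but its listed subgroups include neither CD8 nor PD-L1.

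**The concern.** A Kaplan-Meier analysis needs groups, so the measured value of a continuous marker never reaches the PFS analysis. A patient just above the median counts the same as one at the top of the range. If PFS changes gradually with the marker, the split weakens the signal that the secondary objective is looking for. The cut also depends on the sample, so it need not mean the same thing in another population. No other readable section relates the measured value to outcome. What is at stake is the sensitivity of the exploratory biomarker work, not the primary or OS comparison.

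**Working it through.** **Inputs from the documents.** 289 PFS events, HR 0.68, one-sided 0.025 and at least 90% power (SAP 5.1.1); interim at 217 events (SAP 5.1.2); about 640 patients randomized 1:1 (SAP 2.2); control median PFS 33 months and 22 months of accrual (SAP 5.1.1). No marker effect, marker distribution or biomarker power is stated, so those are assumptions below and are shown as ranges.

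**1. The plan's event base.** Schoenfeld's formula gives 4 × (1.960 + 1.282)² / (ln 0.68)² = 283 events; Freedman's gives 290. With looks at 217 and 289 events and Lan-DeMets O'Brien-Fleming spending, the interim alpha is 0.0097, the interim z is 2.338, the final one-sided p is 0.022 and the power is 90.2%. These match the documents, so 289 is a sound base.

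**2. Information kept by a median split.** When the effect is linear in the marker X, the fraction kept is the squared correlation between X and the indicator that X is at or above its median. For a normal X the correlation is 0.3989 / 0.5 = 0.798 = √(2/π). The square is 2/π = 0.637, a loss of 36.3%. The loss for other assumed distributions, with the effect linear on that scale, is:

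| Assumed distribution | Loss |
|---|---|
| Beta(0.5, 0.5), U-shaped | 19% |
| Uniform | 25% |
| Normal | 36% |
| Beta(0.5, 2) | 43% |
| Lognormal, sigma 0.5 | 48% |
| Exponential | 52% |
| Lognormal, sigma 1 | 73% |

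**3. Power for a marker-by-treatment test, if one were fitted.** With D events, 1:1 allocation, a normal marker and a log-linear effect, power = Φ(|ln r| × √D / 2 − 1.96), where r is the HR ratio per SD (two-sided 0.05). For the split, the first term is multiplied by 0.798. At D = 289, √D / 2 = 8.5. Example at r = 0.75: 0.2877 × 8.5 = 2.445, so the measured scale gives Φ(0.485) = 0.686; the split gives 2.445 × 0.798 = 1.951 and Φ(−0.009) = 0.496.

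| r per SD | Measured scale | Median split | Loss (points) |
|---|---|---|---|
| 0.90 | 14.4% | 10.6% | 4 |
| 0.85 | 28.1% | 19.6% | 9 |
| 0.80 | 47.5% | 32.8% | 15 |
| 0.75 | 68.6% | 49.6% | 19 |
| 0.70 | 85.8% | 67.7% | 18 |
| 0.65 | 95.6% | 83.2% | 12 |
| 0.60 | 99.1% | 93.4% | 6 |

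The largest possible loss under this model is 19.4 points, where measured-scale power is about 75%. Fewer events move that peak to stronger effects (near r = 0.70 at 217 events and 0.65 at 145) without raising it.

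**4. Simulation check.** Cox fits with 640 patients, 289 events and 600 replicates per case gave 29.3% vs 21.5% (r = 0.85), 45.5% vs 32.8% (0.80), 70.0% vs 48.7% (0.75), 86.3% vs 66.5% (0.70) and 94.8% vs 82.0% (0.65). These agree with the table within simulation error of about 2 points per estimate.

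**5. Where the split wins.** If the true relation is a step at the median, simulated power is 62.0% for the split against 46.5% for the measured scale (log-HR shift of ln 0.75 either side), and 27.5% against 20.0% (ln 0.85).

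**6. The same loss without an interaction term.** For a marker-PFS association pooled over arms with HR 1.2 per SD, z = 0.182 × √289 = 0.182 × 17 = 3.10 on the measured scale and 3.10 × 0.798 = 2.47 after the split. Power is about 87% against 70% (two-sided 0.05).

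**7. When the rule breaks down.** The groups are below the median and at or above it. If more than half of the patients share the lowest value, the median equals that value and the lower group is empty. Exactly half is not enough when the number of patients is even, because the averaged median then lies above the lowest value. SAP 6.2.6 gives no fallback.

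**The case against.** The strongest reply is that the analysis is labelled exploratory, carries no alpha and concerns candidate markers. A median cut fixed in advance is blind to outcome and avoids searching for a cut-point. The SAP version history records that the biomarker analysis was deliberately simplified. All of this stands, and it limits the weight of the point. It does not justify leaving the measured value out of the PFS analysis, because a measured-scale model specified in advance is equally free of cut-point searching.

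A reader might infer stronger claims that the documents do not support:
- **That the planned analysis loses a known 36% of information, or a fixed number of power points.** Both figures need a marker distribution and an effect shape, and the power figure also needs an effect size. The documents give none of these.
- **That a planned interaction test is underpowered.** No marker-by-treatment test is planned in the readable text, so step 3 describes a test that would have to be added.
- **That PD-L1 is analysed as a percentage and will fail at 0%.** Table 4 gives no scale, so PD-L1 may fall under the rule for non-continuous markers.
- **That biomarkers are analysed only after the split.** They are also summarised on the measured scale; the restriction applies to the link with PFS.
- **That the figures carry over to the optional on-treatment biopsies.** SAP 4.3.3 limits that set to patients dosed with avelumab who have an on-treatment assessment, so a two-arm calculation on 289 events does not apply.

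Parts of the SAP are redacted, including text under 6.3, and could contain further biomarker analyses. Absence can be stated only for the readable text.

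**Conclusion.** The point holds as a cheap improvement to an exploratory analysis. In the readable text, continuous markers are related to PFS only as below versus at or above the median. This applies to CD8 density and percent, and to PD-L1 only if it is scored continuously. The 36% loss rests on a normal marker with a log-linear effect; across the other distributions tried it ranges from about 19% to 73%. The cost of up to about 19 power points further assumes a marker-by-treatment test at 289 events, and shrinks to about 4 points at an HR ratio per SD of 0.90 and 6 points at 0.60. If the truth is a step near the median, the direction reverses. The empty-group failure needs more than half of the patients at the lowest value. Nothing here affects the primary PFS test.

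**What to change.** In SAP 6.2.6 add, as the main exploratory analysis for each continuous marker, a Cox model for PFS with the marker on its measured scale. Use a log transformation or a restricted cubic spline if the marker is skewed, and a zero indicator if many values are 0. Keep the median-split Kaplan-Meier curves as display, where a step near the median would still show. Whether to add a marker-by-treatment term is a separate decision; the same model could carry one.

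The cost is SAP wording and one extra model per marker, with no new data. A per-SD effect is less simple to show than two curves, which are retained. The analysis stays exploratory.
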